6.1.1.4. Supplementary Analyses

The effect of each dose regimen of HZN-825 will be compared to placebo using the following measurements and methods:

- Change in FVC (in mL) from Baseline to Week 52 using a similar MMRM analysis method as described in the primary analysis method.
- Cumulative response curve that displays a continuous view of the FVC% predicted change from baseline to Week 52 on the X-axis, with Y-axis displaying the proportion of subjects experiencing up to that level of change.
- While On-treatment Strategy for early treatment discontinuation: data collected after the treatment period (date of last dose + 28 days) will be excluded. The same model as for primary analysis will be used after excluding aforementioned data.
- Hypothetical strategy for lung transplant: the FVC% predicted to reflect the treatment
 effect is the value collected when lung transplant had not occurred. The same model
 as for the primary analysis will be used after excluding data collected after lung
 transplant. This analysis will be performed if we have more than three cases of lung
 transplant.
- Hypothetical strategy for rescue medication: the FVC% predicted to reflect the treatment effect is the value collected when rescue medication had not started. The same model as for the primary analysis will be used after excluding data collected after initiation of rescue medication.

6.1.2. Secondary Efficacy Endpoints

6.1.2.1. Key Secondary Endpoint: Proportion of Subjects with Decline in FVC% Predicted ≥10% from Baseline at Week 52

The proportion of subjects with a decrease in FVC% predicted \geq 10% from baseline at Week 52 will be analyzed with observed data using a stratified logistic regression model. Baseline value and treatment will be considered as factors in the model and prior use of approved IPF therapy [yes or no], FVC% predicted at baseline [\geq 70, <70] will be considered as stratification factors.

Version 2.0

The odds ratio between each dose and placebo with its 90% confidence intervals and P-value will be presented. Subjects missing FVC% predicted values at Week 52 will be imputed as non-responders.

The proportion of subjects with a decrease in FVC% predicted ≥10% from baseline predicted will also be summarized descriptively for observed cases at each visit.

6.1.2.2. Change From Baseline in the 6 Minute Walk Test (6MWT) Results to Week 52

The 6MWT measures the distance a subject can quickly walk on a flat, hard surface in 6 minutes (6-minute walk distance). This test evaluates the global and integrated responses of all the systems involved during exercise, including the pulmonary and cardiovascular systems, systemic circulation, peripheral circulation, blood, neuromuscular units and muscle metabolism. The 6MWT will be performed according to American Thoracic Society (ATS) guidelines for the 6MWT (LH, 2018)

The distance walked by the 6MWT will be tested in the same manner as that described for the primary analysis of the primary endpoint in Section 6.1.1.1, but based only on observed data and including the covariate of oxygen flow rate in the model. For subjects who aren't on supplemental oxygen (SpO2) at the visit, 0 liters per minute will be imputed for their oxygen flow rate. Descriptive statistics for the observed results and change from Baseline in the absolute distance walked of the 6MWT will be summarized for each visit.

Values corresponding to the 6MWT including baseline (prior to test) dyspnea, baseline (prior to test) fatigue, baseline (prior to test) SpO2, baseline (prior to test) heart rate, end of test dyspnea, end of test fatigue, end of test heart rate, and end of test SpO2 will be summarized at each visit for the observed results and change from Baseline.

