#### 2.1 **Schedule of Assessments During the Core Phase**

	Screer	ning 		Double-blind Treatment Period									Safety Follow-up Visit		
Trial Visit		1	2	3	4	5	6	7	8	9	10	11	12	13	14 4 weeks after last dose of trial drug
Trial Week (W)	-56 days	-35 days	Day 1 2, 3	W2 	W4	W6 	W10	W16	W22 	W28 	W34 	W40	W46 	W52/PD 3, 6	W56
Visit Window (±days)				(±3)	(±3)	(±3)	(±7)	(±7)	(±7)	(±7)	(±7)	(±7)	(±7)	(±7)	(±14)
Informed consent 	Х														, ,
Lung HRCT (assessed by central review) 8	X													X 9	
Histopathology central review (assessed by central review, if available, but not required) 10	X														
Review eligibility criteria		X	X												
Demographics		X													
Medical, IPF, and substance use history		X	X												
Weight		X	X							X				X	
Height		X													
Randomization 11			X												
Trial drug dispensing			X		X		X	X	X	X	X	X	X	X 12	
Treatment compliance				X	X	X	X	X	X	X	X	X	X	X	
FVC % predicted/spirometry		X	X		X			X		X		X		X	
Titrated oxygen requirement			X					X		X		X		X	
6MWT			X					X		X				X	
DLCO 13		X	X					X		X		X		X	
Patient-reported Outcome Asse	essments														
L-IPF, K-BILD, LCQ, SF-12			X					X		X		X		X	
Anchor Questions															
FVC (last week)			X					X		X		X		X	
FVC (change since start of trial)										X				X	
Pregnancy test 		X	X		X			X		X		X		X	X
Physical examination 15		X	X							X				X	X
Vital signs, including pulse oximetry 16		X	X		X		X	X	X	X	X	X	X	X	X

Date: 07 October 2024

IND 154671

Fipaxalparant (HZN-825) Protocol: HZNP-HZN-825-303 Version 5.0, Amendment 4

	Scree	ning 		Double-blind Treatment Period											Safety Follow-up Visit
Trial Visit		1	2	3	4	5	6	7	8	9	10	11	12	13	14 4 weeks after last dose of trial drug
Trial Week (W)	-56 days	-35 days	Day 1 2,3	W2 	W4	W6 	W10	W16	W22 	W28 	W34 	W40	W46 	W52/PD 3, 6	W56
Visit Window (±days)				(±3)	(±3)	(±3)	(±7)	(±7)	(±7)	(±7)	(±7)	(±7)	(±7)	(±7)	(±14)
Orthostatic hypotension assessment			X		X					X				X	
12-lead electrocardiogram 		X	X		X			X		X				X	
Echocardiogram 		X	71		71			71		71				X	
Laboratory Evaluations									I						
Chemistry and hematology 		X	X		X		X	X	X	X	X	X	X	X	X
Fasting glucose and lipids 			X							X				X	
hsCRP			X							X				X	

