# 9.6.1.3 Primary Efficacy Endpoint Analysis

The estimand for the primary efficacy analyses will be constructed to compare the primary endpoint between each dose regimen of fipaxalparant (HZN-825) and placebo using the treatment policy strategy approach to intercurrent events. All subjects who are randomized and take at least 1 dose of trial drug will be included in the primary efficacy analyses (FAS).

The primary efficacy endpoint will be change from Baseline in FVC % predicted to Week 52. A mixed model for repeated measures (MMRM) analysis of covariance model will be fit to the data using observed change in FVC % predicted values from all planned post-Baseline assessments (i.e., Weeks 4, 16, 28, 40, and 52) with covariates of stratification factors (concomitant use of IPF therapy [yes, no] and FVC % predicted at Baseline [≥70%, <70%]), treatment group, visit and visit-by-treatment group interaction. The unstructured variance-covariance matrix will be used in the model. Treatment group least squares means, associated standard error (SE) and their differences (each fipaxalparant [HZN-825] group minus placebo separately), SE of the difference, 90% CIs and p-value overall and for each visit will be provided.

For subjects with missing data at 1 or more time points, the available data will be included in the analysis.

As a supplemental analysis to assess the robustness of the efficacy analysis results, the effect of each dose regimen of fipaxalparant (HZN-825) will be compared to placebo using the following measurements and methods:

Horizon Therapeutics Ireland DAC (a wholly owned subsidiary of Amgen Inc.) Date: 07 October 2024

IND 154671

Fipaxalparant (HZN-825) Protocol: HZNP-HZN-825-303 Version 5.0, Amendment 4

- Change in FVC (in mL) from Baseline to Week 52 using a similar MMRM analysis method as described for the primary efficacy endpoint
- Cumulative response curve comparison using the Kolmogorov-Smirnov test on:
  - The range of improvement (≥0% to ≥15% with a 5% increment) and worsening (< -15% to <0% with a 5% increment) based on the change in FVC % predicted value from Baseline at Week 52

  - The range cut-off values from less than -300 mL to greater 100 mL with a 100-mL increment based on the change in FVC (in mL) from Baseline at Week 52

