### SUMMARY OF CHANGES **Protocol HZNP-HZN-825-303** Version 4.0 Amendment 3, incorporating Protocol Version 3.0

Key additions, revisions and clarifications to Version 3.0 of the protocol include:

- Updating the Sponsor's address.
- Revising the geographical regions and approximate number of sites in which the trial will be conducted.
- Making this a 2-part study by adding an optional, 52-week open-label extension to the trial (i.e., the Extension Phase [Part 2]). The Core Phase (Part 1) refers to the randomized, double-blind, placebo-controlled part of the trial.
- Clarifying the secondary objective pertaining to safety.
- Removing evaluation of metabolite(s) of HZN-825 in the 9th secondary objective, as this was deemed not necessary by communication with the United States Food and Drug Administration.
- Modifying one of the stratification factors to be *concomitant* use of approved IPF therapy rather than *prior* use and revising statistical analysis accordingly.
- Removing baseline FVC % predicted from statistical models due to the high collinearity with one of the stratification factors in the model.
- Specifying that the first secondary efficacy endpoint is the key secondary efficacy endpoint.
- Updating the p-values in the description of the tipping point analysis.
- Specifying that there will be an interim analysis
- Deleting mention of adjustment to account for the futility analysis. Since there will be a futility analysis during the interim analysis, with no intention to stop the trial due to efficacy evaluation, there is no need to adjust the significant value for multiple comparisons at interim analysis.
- Updating p-values due to updated overall significance level (alpha = 0.10, 2-sided).
- Changing the testing procedure for multiple comparisons from a Hochberg testing procedure to a hierarchical testing procedure.
- Specifying that p-values for other secondary endpoints will not be used for inferential purposes.
- Updating description of the sample size estimate; the target enrollment was reduced to 135 subjects from 360 subjects.
- Modifying inclusion criteria with respect to age, current and initial diagnosis of idiopathic pulmonary fibrosis (IPF), current IPF therapy and diffusing capacity of the lungs for carbon monoxide (DLCO); clarifying inclusion criteria pertaining to lung

Protocol: HZNP-HZN-825-303 IND 154671 Version 4.0, Amendment 3

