6. EFFICACY ANALYSES

6.1. Core Phase

6.1.1. Primary Efficacy Endpoint

6.1.1.1. Primary Analysis Method

The primary efficacy endpoint is the change from Baseline in FVC % predicted at Week 52. The FVC% predicted data are collected at Screening, Day 1, Week 4, Week 16, Week 28, Week 40, and Week 52.

The estimand for the primary efficacy analyses is constructed to compare the primary endpoint between each dose regimen of HZN-825 and placebo, using the treatment policy strategy approach to ICEs without data imputation in FAS subjects.

The primary analysis will be based on a mixed model for repeated measures (MMRM) analysis of covariance (ANCOVA) model using observed change in FVC % predicted values from all planned post-baseline assessments (Weeks 4, 16, 28, 40 and 52) with covariates of treatment group (300 mg HZN-825 QD, 300 mg HZN-825 BID, placebo), prior use of IPF therapy [yes or no], FVC% predicted at baseline [≥ 70, <70], visit week, and treatment by visit week interaction. An unstructured covariance matrix will be used as the primary analysis method; if the model does not converge, the following three variance-covariance matrices or by visit week will be attempted in order until one converges: heterogeneous Toeplitz (TOEPH), heterogeneous compound symmetry (CSH), and Toeplitz (TOEP).

Treatment group least squares means, associated standard error (SE) and their differences (each HZN-825 group minus placebo separately), SE of the difference, 90% CIs and p-values for each visit will be provided with Week 52 estimands being the primary efficacy endpoint result. A line plot of the LS mean value for FVC% predicted change from Baseline will be plotted by treatment group for each visit week over time, including the estimated 90% CI around each LS mean.

Change in FVC % predicted will also be summarized descriptively for observed cases at each visit.

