6.1.2.3. Change from Baseline in King's Brief Interstitial Lung Disease (K-BILD)
Questionnaire Total Score to Week 52

The K-BILD is a self-completed health status questionnaire comprising 15 items, each with a 7-point Likert response scale that was developed and validated specifically for patients with IPF (Patel AS, 2012). The response options vary, but in general 1 = worst disease impact and 7 = least disease impact. This questionnaire has 3 domains: psychological, breathlessness and activities and chest symptoms. The K-BILD domains and total score range from 0 to 100; 100 represents best health status.

The K-BILD scoring has recently changed with the introduction of a logit transformation step. The minimal clinically important difference for the K-BILD total score (logit version), as determined by both anchor and distribution-based methods, is a change of 5 units [Sinha et al., 2019].

The K-BILD total score will be tested in the same manner as that described for the primary analysis of the primary endpoint in Section 6.1.1.1, but based only on observed data.

Version 2.0

Descriptive statistics for the observed results and change from Baseline in the K-BILD total score and each domain score will be summarized for each visit.

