6.1.2.4. Change from Baseline in the Living with Pulmonary Fibrosis (L-IPF)
Questionnaire Symptoms Total and Impacts Total Score to Week 52

The L-IPF is a validated questionnaire that assesses symptoms, disease impacts and health-related quality of life in subjects with IPF (Swigris JJ, 2020). This questionnaire was developed with input from the FDA and comprises 2 modules: a 15-item symptom module with 3 domains (dyspnea, cough and energy), all with a 24-hour recall, and a 20-item impacts module with 1-week recall. All items in both modules have response options in a 5-point (0-4) numerical rating scale format. The L-IPF yields five scales (symptoms total, dyspnea, cough, energy, and impacts total); raw scores for each are transformed to a model-based scale ranging from 0 to 100 with a mean of 50 and an SD of 10. For each scale, tables are used to convert raw scores, and higher scores indicate greater impairment.

The absolute change from Baseline in the L-IPF impacts total score, the L-IPF symptoms total score at week 52 will be computed and evaluated in the same manner as that described for the primary analysis of the primary endpoint in Section 6.1.1.1 but based only on observed data. Descriptive statistics for the observed results and change from baseline in the the L-IPF impact score, the L-IPF symptoms total score and the L-IPF symptoms domain scores will be summarized for each visit.

6.1.2.5. Change from Baseline in Leicester Cough Questionnaire (LCQ) Total Score to Week 52

The LCQ is a patient-reported questionnaire evaluating the impact of cough on quality of life. This questionnaire was originally developed for use in people with idiopathic chronic cough and has since been validated for use in people with bronchiectasis and chronic obstructive pulmonary disease (Birring SS, 2003).

The LCQ comprises 19 items and takes 5 to 10 minutes to complete. Each item assesses symptoms or the impact of symptoms over the last 2 weeks on a 7-point Likert scale. Scores in 3 domains (physical, psychological and social) are calculated as a mean for each domain (range: 1 to 7). A total score (range: 3 to 21) is also calculated by summing the domain scores. Higher scores indicate better quality of life.

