The LCQ total score will be tested in the same manner as that described for the primary analysis of the primary endpoint in Section 6.1.1.1, but based only on observed data. Descriptive statistics for the observed results and change from Baseline in the LCQ total score and each domain score will be summarized for each visit.

6.1.2.6. Time to First Hospitalization Due to Respiratory Distress from Baseline up to Week 52

Hospitalization due to respiratory distress is defined as a non-elective hospitalization lasting more than 24 hours in a hospital, emergency room or observation unit, due to respiratory

Version 2.0

causes that occur after randomization. Adverse events identified as leading to hospitalization due to respiratory distress will be adjudicated to confirm that the event and hospitalization meet the stated criteria.

A Cox proportional hazard model stratified by prior use of approved IPF therapy [yes or no] and FVC% predicted at baseline [\geq 70, <70] and treatment group as factors will provide the hazard ratio, its 90% CI and p-value to compare each HZN-825 group with the placebo group.

A subject will be considered as meeting the event criteria if the adjudication committee identifies any adverse event as leading to hospitalization due to respiratory distress. The start date of the hospitalization will be day of the event. In all other cases, the subject will be considered censored, and their last date of contact in the study (either date of safety follow-up if the subject doesn't enter the extension study or the Week 52 visit date for subjects that enter the extension) will be the date of censoring.

A corresponding Kaplan-Meier plot will be created to supplement the analysis, along with a summary of the quartiles of the Kaplan-Meier time to event estimate.

6.1.2.7. Composite Endpoint: Progression Free Survival (PFS) from Baseline up to Week 52, where Progression Includes Decline in FVC % Predicted ≥ 10% or Death

A Cox proportional hazard model stratified by concomitant use of approved IPF therapy [yes or no] and FVC% predicted at baseline [\geq 70, <70] and treatment group as factors will provide the hazard ratio, its 90% CI and p-value to compare each HZN-825 group with the placebo group.

[figure not shown]

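### The MMRMs for 6MWT, K-BILD, L-IPF and LCQ omit each outcome's own Day 1 baseline, at a modest and avoidable cost in precision

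*SAP*

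**What the plan says.** **Primary model.** Besides treatment, SAP 6.1.1.1 lists "prior use of IPF therapy [yes or no], FVC% predicted at baseline [≥ 70, <70], visit week, and treatment by visit week interaction". There is no continuous baseline. Protocol 9.6.1.3 is built the same way, "with covariates of stratification factors (concomitant use of IPF therapy [yes, no] and FVC % predicted at Baseline", again as a two-level category. The Amendment 3 summary of changes gives the reason: "Removing baseline FVC % predicted from statistical models due to the high collinearity with one of the stratification factors in the model".

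**Continuous secondaries.** For the walk test, SAP 6.1.2.2 states: "The distance walked by the 6MWT will be tested in the same manner as that described for the primary analysis of the primary endpoint". It adds only oxygen flow rate to that model. For K-BILD, "The K-BILD total score will be tested in the same manner as that described for the primary" analysis. The L-IPF symptoms and impacts totals "will be computed and evaluated in the same manner as that described for the primary analysis of the primary endpoint". For the cough questionnaire, "The LCQ total score will be tested in the same manner as that described for the primary" analysis. Protocol 9.6.1.4 also models these outcomes by analogy with the primary. The Core Phase schedule (Protocol 2.1) has the walk test and the row "L-IPF, K-BILD, LCQ, SF-12" on Day 1. SAP 3.4 makes the p-values of these endpoints non-inferential.

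**Related models.**
- Key secondary: SAP 6.1.2.1 puts a baseline value in the logistic model and stratifies by prior antifibrotic use and FVC category. Protocol 9.6.1.4 has treatment and the randomisation strata only. The SAP (version 2.0, 16 August 2024) is based on protocol 4.0; protocol 5.0 (07 October 2024) still has no baseline term.
- Cox models: SAP 6.1.2.6 (hospitalisation) stratifies by prior use and SAP 6.1.2.7 (PFS) by concomitant use. Protocol 9.6.1.4 gives both the logistic model's strata.
- SAP 2.5 declares the move from concomitant to prior use, naming the MMRM. It does not mention the key secondary baseline term.

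**The concern.** In an analysis of change, the outcome's own baseline is usually among its strongest predictors: subjects who start high tend to fall more, through regression to the mean. Leaving it out puts that variation into the residual and leaves the estimate open to chance imbalance. With 45 per arm, a baseline imbalance of one standard error is √(2/45) = 0.21 SD. It shifts an unadjusted comparison of changes by (1 − ρ) × 0.21 SD, that is 0.11 SD at ρ = 0.5 and 0.02 SD at ρ = 0.9.

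The stated reason for the omission concerns baseline FVC and its own category. Walk distance and questionnaire scores are different variables, so the reason does not carry over. Nor does the SAP hold to it throughout: the key secondary model has both a baseline value and the FVC category, and the multiple imputation in 6.1.1.3 uses baseline FVC together with the strata.

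At stake is precision on four descriptive secondary outcomes. Separately, the two current documents give different models for the key secondary, which is in the testing hierarchy.

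**Working it through.** **Inputs from the documents.** 45 per arm, difference 3, SD 9 (SAP 1.3); two-sided α = 0.10 (SAP 3); walk test at Weeks 16, 28 and 52 and questionnaires at Weeks 16, 28, 40 and 52 (Protocol 2.1).

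**Assumed, not in the documents.** The correlation ρ of baseline with Week 52; the ratio k of Week 52 SD to baseline SD; the baseline FVC distribution.

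**1. The plan's own figures.** SE = 9√(2/45) = 1.897. Then Φ((3−1)/1.897) = 85.4%, Φ((3−2)/1.897) = 70.1% and 1 − Φ(2/1.897) = 14.6%. The stated 85, 70 and 15% reproduce. They are probabilities that a point estimate passes a threshold. Power of the 0.10-level test at difference 3 is Φ(3/1.897 − 1.645) = 47.5%.

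**2. Secondary MMRMs with own baseline and a slope per visit.** With baseline SD s, Var(change) = s²(1 + k² − 2ρk) and Cov(change, baseline) = s²(ρk − 1). The share of Week 52 variance removed is (ρk − 1)²/(1 + k² − 2ρk). At k = 1 this is (1 − ρ)/2, so the variance ratio is VR = (1 + ρ)/2. Estimating the slope costs about 1/(135 − 5 − 2) = 0.8% of variance.

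| ρ | VR | CI narrowing, 1 − √VR | Patients per arm, gross, 45/VR − 45 | Net, 45/(1.0078 × VR) − 45 |
|---|---|---|---|---|
| 0.5 | 0.75 | 13.4% | 15.0 | 14.5 |
| 0.7 | 0.85 | 7.8% | 7.9 | 7.5 |
| 0.9 | 0.95 | 2.5% | 2.4 | 2.0 |

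Charging the slope cost to the interval as well gives 13.1, 7.4 and 2.2%. A simulation of Week 52 change (three arms of 45, prior use and FVC category in both models) gave SE reductions of 12.5, 7.0 and 2.0%. The walk test's oxygen flow term and dropout are ignored throughout.

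**3. Where the gain shrinks.** With one common slope and correlation decaying as ρ^(weeks apart/52), variance falls by 19, 10 and 3%, worth 10.5, 4.9 and 1.3 patients per arm before the slope cost. At k = 1.25 and ρ = 0.8, ρk − 1 = 0: baseline explains nothing and the added terms cost about 0.8% of variance.

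**4. Primary MMRM, for comparison.** With change SD fixed at 9, baseline FVC SD 12 to 18, mean 70 to 80 and k from 1.0 to 1.25, baseline-by-visit terms explain 0 to 7.7% of Week 52 variance beyond the category. Net VR runs from 1.0078 to 0.923 × 1.0078 = 0.930. Power = Φ(3/(1.897√VR) − 1.645) runs from 47.2% to 49.8%, against 47.5% now.

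**5. Related models.**
- Key secondary, with and without the baseline term, over 81 assumed scenarios (placebo event rate 15 to 35%): the odds ratio differs by 0 to 3% (largest gap 0.564 against 0.546) and the z statistic by 0 to 2.5%.
- PFS stratified by prior instead of concomitant use, simulated under assumed stratum sizes and event rates: information changes by −0.7% to +0.2%.
- Coding of prior use: SAP 4.1 lets the IRT value govern, which settles subjects stratified on prior use before protocol 4.0. For later enrollees on current therapy, inclusion criterion 4 (at least three months' stable dosing before Day 1) points to yes, while the prior-medication definition in SAP 7.4.1 (ended before first dose) points to no. SAP 2.5 says such subjects are few and gives no count; 5 to 10% (assumed) would be about 7 to 14 of 135.

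**The case against.** The secondary models do what the protocol asks, their p-values carry no inference, and every efficiency figure rests on correlations that the documents do not supply. The FVC category and prior use already absorb a little of the same variation, and missing Week 52 data would reduce the patient equivalents. All of that stands, and it keeps the point modest. It does not supply a reason for the omission: the data are already collected and the worst case costs under 1% of variance.

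On antifibrotic use, a reader might infer that the switch to prior use was concealed. The documents do not support that. SAP 2.5 introduces the change under efficacy analysis and explains it, and the rank ANCOVA, logistic and hospitalisation models state prior use openly. Only the list in 2.5 is incomplete. Concomitant use in the PFS model also matches the current randomisation factor. The difficulty there is inconsistency within the SAP, because its reason for dropping concomitant use, too few users, applies equally to PFS.

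**Conclusion.** The point holds for the four continuous secondary outcomes, as a matter of precision. The omission and the inapplicable reason can be read directly from the text. The size, about 13, 8 or 2.5% in interval width, assumes ρ of 0.5, 0.7 or 0.9, equal variances, a slope per visit and 45 observed per arm. It is smaller with a common slope and can be nil.

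Two stronger readings are tempting. One is that the results are biased or the error rate inflated. Omitting a baseline covariate does not in itself bias a randomised comparison, and these endpoints lie outside the tested hierarchy. The other is that the primary analysis is deficient for want of continuous baseline FVC. That is a declared protocol decision, retained in version 5.0, and reversing it moves power only from 47.5% to between 47.2 and 49.8%, so it might even lose slightly.

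The key secondary discrepancy is real but small in effect. It matters because a hierarchy endpoint should have one stated model. Aligning the PFS stratum brings consistency and no material precision. The prior-use coding rule fills a missing detail.

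**What to change.** Before Core Phase unblinding, by staff who have not seen the interim results:

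1. Add each outcome's own continuous baseline and its baseline-by-visit interaction to the MMRMs for 6MWT, K-BILD, both L-IPF totals and LCQ.
2. State one key secondary model in both documents. If the baseline value stays, list it in SAP 2.5, together with prior use in the rank ANCOVA, logistic and hospitalisation Cox models.
3. Use the same antifibrotic stratum in both Cox models; prior use would match the SAP's logistic model.
4. Define how current users enrolled under protocol 4.0 or later are coded for prior use.

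Continuous baseline FVC in the primary MMRM is optional. If it is adopted, keep the category and declare the departure.

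The cost is SAP wording, a documented pre-unblinding change, and 3 degrees of freedom for the walk test or 4 for each questionnaire score (5 for FVC, if adopted). If baseline explains nothing, about 0.8% of variance is lost. No new data are needed.
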